### 3 Statistical Considerations

#### 3.1 Statistical Hypotheses

All analyses will be descriptive; no hypotheses are planned to be tested.

#### 3.2 Sample Size Determination

Assuming a dropout rate of approximately 10%, a total of approximately 630 participants evaluable for immunogenicity is anticipated.

No study power was calculated for this study. However, examples were given in the table below showing the probability of 2-sided 95% lower being greater than the CBER thresholds (1), if the proportion of participants with HAI antibody titer  $\geq 1:40$  reach a certain proportion; or if the proportion of participants with seroconversion reach a certain proportion.

Table 3.1 shows the expected number of evaluable participants in each study group and each age stratum, and the probability that the lower bound of the 95% CI exceeding the threshold defined by Center for Biologics Evaluation and Research (CBER) requirement for seroconversion and percentage of participants achieving an HAI antibody titer  $\geq 1:40$  (1).

**Table 3.1: Probability of exceeding the CBER lower bound if a certain proportion is achieved**

Age in Years	Evaluable Number of Participants (Study Group)	Expected Proportion	CBER: Lower Bound of 2-Sided 95% CI Greater Than	Probability (%)
Percentage of participants with HAI antibody titer <math>\geq 1:40</math>				
$\geq 18$	270 (Groups 1 or 2)	0.80	70%	96%
18 to $< 65$	135 (Groups 1 or 2)	0.82	70%	88%
$\geq 65$	135 (Groups 1 or 2)	0.72	60%	82%
$\geq 18$	90 (Group 3)	0.85	70%	93%
18 to $< 65$	45 (Group 3)	0.85	70%	< 80%
$\geq 65$	45 (Group 3)	0.80	60%	83%
Percent of participants with seroconversion for antibody				
$\geq 18$	270 (Groups 1 or 2)	0.50	40%	90%
18 to $< 65$	135 (Groups 1 or 2)	0.52	40%	< 80%

Age in Years	Evaluable Number of Participants (Study Group)	Expected Proportion	CBER: Lower Bound of 2-Sided 95% CI Greater Than	Probability (%)
≥ 65	135 (Groups 1 or 2)	0.42	30%	82%
≥ 18	90 (Group 3)	0.55	40%	80%
18 to < 65	45 (Group 3)	0.70	40%	97%
≥ 65	45 (Group 3)	0.50	30%	<80%

### 3.3 Populations for Analyses

For the purposes of analysis, the following analysis sets are defined:

Participant Analysis Set	Description
Randomized	All participants randomized by study IRT to one of the 3 study doses (one of three study groups).
Safety Analysis Set (SafAS)	Participants who have received at least one study intervention.  All participants will have their safety analyzed after each dose according to the intervention received, and after any dose according to the intervention received at the 1st dose. Safety data recorded for a vaccine received out of the protocol design will be excluded from the analysis (and listed separately).
Full analysis set (FAS)	Subset of randomized participants who received at least 1 dose of the study vaccine and had a post-vaccination blood sample for D22 or D43.  Participants will be analyzed according to the study dose group to which they were randomized.
Per-protocol analysis set (PPAS)	To be able to compare and present the results of immunogenicity in the same table, only one PPAS will be derived in this study.  Subset of the FAS participants. Participants presenting with at least one of the following relevant protocol conditions will be excluded from the PPAS: 
 
• Participant did not meet all protocol-specified inclusion criteria or met at least one of the protocol-specified exclusion criteria
 
• Participant did not complete the vaccination schedule
 
• Participant received a vaccine other than the one that he / she was randomized to receive
 
• Preparation and / or administration of vaccine was not done as per-protocol
 
• Participant did not receive vaccine in the proper time window
 

Participant Analysis Set	Description
	

• Participant did not provide a post-dose serology sample at D22 (+7 days) and D43 (+7 days) in the proper time window or a post-dose serology sample was not drawn

• Participant received a medication impacting or that may have an impact on the immune response as described in Section 6.8 of the protocol.

• Re-randomized participants

 
Any other deviation identified during the study conduct and judged by the clinical team during data review as having a potential impact on the assessment of immunogenicity will be used to exclude a participant from the PPAS. These deviations will be determined during the protocol deviations review and will be flagged for excluding a participant from PPAS.
 
In the event of a local or national immunization program with a SARS-CoV-2 or other vaccine, participants who receive 1 or more doses of the vaccine listed above at any time during the study will not be withdrawn from the study.

## 3.4 Statistical Analyses

The SAP Core Body should be used in conjunction with the study protocol and the SAP TLFs. The Core Body and TLFs are available before the first interim analysis (without considering SMT analysis).

### 3.4.1 General Considerations

The statistical analysis referring to primary and secondary objectives will be performed under the responsibility of the Sponsor's Biostatistics platform using SAS® Version 9.4 or later.

The statistical analysis will be conducted as follows:

- The database will be locked, and the study will be unblinded after all immunogenicity and safety data are collected for the follow-up period of 3 weeks after D22 (i.e., 21 days after the last vaccination).
- The final database lock will occur after the 12-month follow-up.

No adjustment for multiplicity regarding multiple comparisons between study doses is planned in this study.

For descriptive purposes, the following statistics will be presented:

**Table 3.2: Descriptive statistics produced**

Baseline characteristics and follow-up description	Categorical data	Number and percentage of participants
	Continuous data	Mean, standard deviation, quartiles, minimum, and maximum
Safety results	Categorical data	Solicited: Number and percentage (95% confidence intervals [CIs]) of participants Unsolicited: Number and percentage (95% CIs) of participants, and number of events
	Continuous data	At least mean, standard deviation, minimum, and maximum
Immunogenicity results	Categorical data (seroprotection, seroconversion, cutoff)	Number and percentage (95% CIs) of participants
	Continuous data (titer / data)	$\text{Log}_{10}$ : Mean and standard deviation $\text{Anti-Log}_{10}$ (work on $\text{Log}_{10}$ distribution, and $\text{anti-Log}_{10}$ applied): Geometric mean, 95% CI of the geometric mean, quartiles, minimum, and maximum Graphical representation by Reverse Cumulative Distribution Curve (RCDC) Graphical representation showing geometric mean titer (GMT) kinetics Graphical representation showing boxplot

The confidence interval (CI) for the single proportion will be calculated using the exact binomial method (Clopper-Pearson method, quoted by Newcombe (2), i.e., using the inverse of the beta integral with SAS®).

For immunogenicity results, assuming that  $\text{log}_{10}$  transformation of the titers / data follows a normal distribution, at first, the mean and the 95% CI will be calculated on  $\text{log}_{10}$  (titers / data) using the usual calculation for normal distribution (using Student's t distribution with  $n-1$  degree of freedom), then antilog transformations will be applied to the results of calculations, in order to provide geometric means (GMs) and their 95% CI.

### 3.4.2 Primary Endpoints

#### Primary Immunogenicity Objective

The immunogenicity parameters will be calculated with their 95% CIs using the exact binomial distribution (Clopper-Pearson method) for proportions and using normal approximation of log-transformed for GMs and GMs ratio. The 95% CI of proportions difference (i.e., difference between vaccine groups in seroconversion) will be calculated using Wilson Score method without continuity correction (3). All analyses will be conducted by study group and by age stratum.

The time windows used for collecting blood samples are: D01, D22 [+7], D43 [+7], D202 [+14], and D387 [+14]. To avoid redundancy and typing errors, these time windows will not be reported in all sections of this document.

- Immunogenicity by HIH measurement method
  - GMTs of HAI Ab titers obtained on D01, D22, D43, D202, and D387
  - Geometric mean of individual ratios of HAI Ab titers D22/D01, D43/D01, D202/D01, D387/D01, D22/D202, D22/D387, D202/D43 and D387/D43
  - Percentage of participants with seroconversion defined as HAI Ab titer < 10 (1/dilution [1/dil]) on D01 and post-injection titer  $\geq$  40 (1/dil) on D43 or defined as titer  $\geq$  10 (1/dil) on D01 and a  $\geq$  4-fold increase in titer (1/dil) on D43.  
Percentage of participants with seroconversion defined as HAI Ab titer < 10 (1/dilution [1/dil]) on D01 and post-injection titer  $\geq$  40 (1/dil) on D22 or defined as titer  $\geq$  10 (1/dil) on D01 and a  $\geq$  4-fold increase in titer (1/dil) on D22.  
The interpretation of the results will account for seroconversion thresholds reported in FDA guideline (1) for participants 18 – 64 years and  $\geq$  65 years of age.
  - Percent of participants with HAI Ab titers  $\geq$  40 (1/dil) on D22, and percent of participants with HAI Ab titers  $\geq$  40 (1/dil) on D43. The same statistic will be calculated for D01, D202, and D387.  
The interpretation of the results will account for sero-protection thresholds reported in FDA guideline (1) for participants 18 – 64 years and  $\geq$  65 years of age.
  - Percent of participants with detectable HAI Ab titer  $\geq$  10 (1/dil) on D01, D22, D43, D202, and D387.
  - Difference and its 95% CI in seroconversion between the 3 study doses (Group 1 - Group 3; Group 2 - Group 3, and Group 2 - Group 1) at D22 and D43.
  - Ratio of GMTs and its 95% CI for: Group1/Group3, Group2/Group3, and Group2/Group1 at D22, and at D43.
  - The RCDCs of pre-vaccination titer prior to the first vaccination (D01), and post-vaccination titer at D22, D43, D202, and D387 will be generated for each study dose.  
The RCDCs will include the plots of the 3 doses on the same figure.
- Immunogenicity by SN measurement method
  - GMTs of NT Ab titer obtained on D01, D22, D43, D202 and D387.
  - Geometric mean of individual ratios of NT Ab titers D22/D01, D43/D01, D202/D01, D387/D01, D22/D202, D22/D387, D202/D43 and D387/D43
  - Percentage of participants with NT Ab titers  $\geq$  20 (1/dil),  $\geq$  40 (1/dil),  $\geq$  80 (1/dil) on D01, D22, D43 D202 and D387.
  - Percent of participants with fold increase in NT Ab titer [D43/pre-vaccination]  $\geq$  2 and  $\geq$  4 on D43

Percent of participants with fold increase in NT Ab titer  $[D22/\text{pre-vaccination}] \geq 2$  and  $\geq 4$  on D22

- Percent of participants with detectable NT Ab titer  $\geq 10$  (1/dil) on D01, D22, D43, D202, and D387.
- Difference and its 95% CI in percentage of participants with fold increase between the 3 study doses (Group 1 - Group 3, Group 2 - Group 3, and Group 2 - Group 1) on D22, and on D43.
- Ratio of GMs and its 95% CI for: Group1/Group3, Group2/Group3, and Group2/Group1 on D22, and on D43.
- The RCDCs of pre-vaccination titer prior to the first vaccination (D01) and post-vaccination titer at D22, D43, D202, and D387 will be generated for each study dose. The RCDCs will include the plots of the three doses on the same figure.

For each immunogenicity measurement method, the analysis will be conducted for each immunogenicity variable on the PPAS and the FAS.

In addition, subgroup analysis will be performed on FAS; in, immunogenicity will be described according to sex, race, age subgroups and sero-status at baseline as appropriate according to number of participants in the respective subgroup(s).

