## 6.3 Measures to Minimize Bias: Randomization and Blinding

### 6.3.1 Randomization and Allocation Procedures

Randomization of participants will be performed with the blocked method, with stratification by age stratum. Each participant who meets all the inclusion criteria and none of the exclusion criteria and signs the ICF will be randomly assigned according to the participant's age group, to either Group 1, Group 2, or Group 3 via an interactive response technology (IRT) system, according to a 3:3:1 ratio.

Before vaccination, authorized qualified study staff will connect to the IRT system, enter the identification and security information, and confirm a minimal amount of data in response to IRT system prompts. The IRT system will then provide the vaccine dose identification number. Participant numbers and vaccine dose identification numbers will be recorded in the eCRF.

The full detailed procedures for group allocation are described in the IRT User Guide. If the participant is not eligible to participate in the study, then the information will only be recorded on the participant recruitment log.

If the dose initially allocated for vaccination cannot be used (eg, because the syringe broke or particulate matter was observed), authorized qualified study staff will obtain a replacement dose. Thus, the site personnel must contact the IRT system to receive the replacement dose allocation.

Participant numbers that are assigned by the IRT will consist of a 12-digit string (a 3-digit country identifier, a 4-digit study center identifier, and a 5-digit participant identifier). For example,

Participant 840000100005 is the fifth participant enrolled in Center Number 1 in the US (840 being the US country code).

Participant numbers should not be reassigned for any reason. The randomization codes will be kept securely in the IRT and an internal system.

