#### 9.4.2 Primary Endpoints

##### Primary Immunogenicity Objective:

The immunogenicity parameters will be calculated with their 95% CIs using the exact binomial distribution (Clopper-Pearson method) for proportions and using normal approximation of log-transformed for GMTs and GMTs ratio. The 95% CI of proportions difference (ie, difference between vaccine groups in seroconversion) will be calculated using Wilson Score method without continuity correction ([19](#)). All analyses will be conducted by study group and also by age stratum.

The time windows used for collecting blood samples are: D01, D22 [+7], D43 [+7], D202 [+14], and D387 [+14]. To avoid redundancy and typing errors, these time windows will not be reported in all sections of this document.

- Immunogenicity by HIH measurement method
  - GMTs of HAI Ab titers obtained on D22, and on D43 for comparison with D01, D202, and D387.
  - Geometric mean of individual ratios of HAI Ab titers D22/D01 and D43/D01; and D202/D01 and D387/D01.
  - Percent of participants with seroconversion defined as HAI Ab titer < 10 (1/dilution [1/dil]) on D01 and post-injection titer  $\geq$  40 (1/dil) on D22 or D43; or defined as HAI Ab titer  $\geq$  10 (1/dil) on D01 and a  $\geq$  4-fold increase in titer (1/dil) on D22 or D43.  
The interpretation of the results will account for seroconversion thresholds reported in FDA guideline ([18](#)) for participants 18 – 64 years and  $\geq$  65 years of age.
  - Percent of participants with HAI Ab titers  $\geq$  40 (1/dil) on D22, and percent of participants with HAI Ab titers  $\geq$  40 (1/dil) on D43. The same statistic will be calculated for D01, D202, and D387.  
The interpretation of the results will account for seroconversion thresholds reported in FDA guideline ([18](#)) for participants 18 – 64 years and  $\geq$  65 years of age.
  - Percent of participants with detectable HAI Ab titer with a titer  $\geq$  10 (1/dil) on D01, D22, D43, D202, and D387.
  - Difference and its 95% CI in seroconversion between the 3 study doses (Group 1 - Group 3; Group 2 - Group 3, and Group 2 - Group 1) at D22 and D43.
  - Ratio of GMTs and its 95% CI for: Group1/Group3, Group2/Group3, and Group2/Group1 at D22, and at D43.

- The RCDCs of pre-vaccination titer prior to the first vaccination (D01), and post-vaccination titer at D22, D43, D202, and D387 will be generated for each study dose. The RCDCs will include the plots of the 3 doses on the same figure.

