- Immunogenicity by SN measurement method
  - GMTs of NT Ab titer obtained on D22, and on D43 for comparison with D01, D202, and D387.
  - Geometric mean of individual ratios of NT Ab titer for D22/D01, D43/D01, D202/D01, and D387/D01.
  - Percentage of participants with NT Ab titers  $\geq 20$  (1/dil),  $\geq 40$  (1/dil),  $\geq 80$  (1/dil) on D22, and on D43; compared to D01, D202, and D387.
  - Percent of participants with fold increase in NT Ab titer [post-vaccination/ pre-vaccination]  $\geq 2$  and  $\geq 4$  on D22 and D43.
  - Percent of participants with detectable NT Ab titer  $\geq 10$  (1/dil) on D01, D22, D43, D202, and D387.
  - Difference and its 95% CI in percent of participants with fold increase between the 3 study doses (Group 1 - Group 3, Group 2 - Group 3, and Group 2 - Group 1) on D22, and on D43.
  - Ratio of GMs and its 95% CI for: Group1/Group3, Group2/Group3, and Group2/Group1 on D22, and on D43.
  - The RCDCs of pre-vaccination titer prior to the first vaccination (D01) and post-vaccination titer at D22, D43, D202, and D387 will be generated for each study dose. The RCDCs will include the plots of the three doses on the same figure.

For each immunogenicity measurement method, the analysis will be conducted for each immunogenicity variable on the PPAS and on FAS.

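### Optional gain: the all-ages GMT ratios leave out the age stratum used in randomisation, so their valid intervals may be slightly wider than they need to be

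*SAP*

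**What the plan says.** Protocol 6.3.1 sets the design: "Randomization of participants will be performed with the blocked method, with stratification by age stratum". The plan is 350 participants in each age stratum, so each group should split evenly by age.

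Protocol 9.4.2 lists the between-group comparisons. For HIH it is "Ratio of GMTs and its 95% CI for: Group1/Group3, Group2/Group3, and Group2/Group1 at D22, and at D43"; for SN it is "Ratio of GMs and its 95% CI for: Group1/Group3, Group2/Group3, and Group2/Group1 on D22, and on D43". SAP 3.4.2 repeats both. The intervals are to be calculated "using normal approximation of log-transformed for GMs and GMs ratio". Neither document names a model, a covariate or a stratum term for these ratios.

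On the level of reporting, Protocol 9.4.2 says "All analyses will be conducted by study group and also by age stratum". The matching SAP sentence omits the word *also*. Protocol Table 9.2 and SAP Table 3.1 have rows for everyone aged 18 or over (270 evaluable in Group 1 or 2, 90 in Group 3) beside the rows for each stratum. Together these imply an all-ages ratio next to the age-specific ones, although no sentence states it outright.

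**The concern.** When allocation is stratified, the design balances age between groups. An interval that ignores the stratum still counts the spread between age groups as random noise. If older participants respond less, as Protocol 4.2 anticipates when it cites immunosenescence, the all-ages interval is wider than the design warrants.

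The D43 analysis is to help select the dose formulation (Protocol 9.5, SAP 3.5), and these ratios are part of that descriptive package. The comparisons with Group 3, at about 90 evaluable, are the least precise. What is at stake is a little precision. The age-specific ratios already condition on age and the differences in proportions are a separate matter; neither is part of this point.

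**Working it through.** **1. The plan's own figures.** 700 × 0.90 = 630 evaluable: 270, 270 and 90 by group, or 135, 135 and 45 per stratum. For each row of SAP Table 3.1, I took the smallest count whose Clopper-Pearson lower bound exceeds the threshold, then the binomial probability of reaching it. All twelve rows agree: for example 95.7% against the stated 96% (n = 270, 0.80), 87.7% against 88% (n = 135, 0.82) and 81.7% against 82% (n = 135, 0.72). The three rows given as below 80% come to 63.9%, 79.1% and 72.4%. The documents give no precision figure for a GMT ratio, so there is none to reproduce.

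**2. General formula.** Take two equal strata and an age gap of d within-stratum SDs in both groups. The spread between strata adds d²/4 to a within-stratum variance of 1, so

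unadjusted width / adjusted width = sqrt(1 + d²/4).

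| d | Excess width of the unadjusted interval |
|---|---|
| 0 | 0.0% |
| 0.2 | 0.5% |
| 0.5 | 3.1% |
| 1.0 | 11.8% |

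**3. Illustration from SAP Table 3.1.** Assume normal log titers with a common within-stratum SD. Then d = z(p, 18-64) − z(p, 65 or over), where z is the normal quantile.

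| Rows | Groups 1 or 2 | Group 3 |
|---|---|---|
| HAI titer ≥ 1:40 | 0.82 v 0.72, d = 0.3325 | 0.85 v 0.80, d = 0.1948 |
| Seroconversion | 0.52 v 0.42, d = 0.2520 | 0.70 v 0.50, d = 0.5244 |

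*Group2/Group1* uses only the Group 1 or 2 rows:
- HAI rows: sqrt(1 + 0.3325²/4) = 1.0137, or 1.4% wider.
- Seroconversion rows: sqrt(1 + 0.2520²/4) = 1.0079, or 0.8% wider.

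*Group1/Group3 and Group2/Group3* need each group's own gap. With pooled variance, relative to the within-stratum variance:
- HAI rows: sqrt[(270 × 1.0276 + 90 × 1.0095)/360] = 1.0115.
- Seroconversion rows: sqrt[(270 × 1.0159 + 90 × 1.0687)/360] = 1.0144.

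A linear model with one common age term does not remove the part of the gap that differs between groups. Against that model, simulation (20,000 trials per case) gives 1.1% (HAI rows) and 1.3% (seroconversion rows). For Group2/Group1 it gives 1.4% and 0.8%. All three contrasts therefore lie at about 0.8% to 1.4%.

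**4. Validity.** In the same simulations the unadjusted interval covers 95.2% to 95.4% and the adjusted one 95.0% to 95.3%. Over-coverage becomes plain only at larger gaps: 95.8% at a common d of 0.5 and 97.3% at 1.0, against 95.1% adjusted in both cases. At d = 0 the two widths agree.

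**5. What it looks like.** Assume an SD of 0.5 log10 (not in the documents), d = 0.3325, and Group2/Group1 with 270 v 270. The 95% factor is ×/÷1.2181 unadjusted and ×/÷1.2149 adjusted. A ratio of 2.00 would have an interval of 1.64 to 2.44 (2.00/1.2181 and 2.00 × 1.2181) against 1.65 to 2.43.

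**The case against.** The strongest reply is that nothing depends on this. No hypothesis is tested, no decision rule uses the interval, and the primary objective is framed within the two age groups, where age is already dealt with. A simple descriptive ratio is a legitimate choice, and the SAP's separate tables, listings and figures, which are not among the documents, may settle the matter. All of that stands. It limits the point to an optional gain but does not show it to be wrong.

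The second reply concerns the inputs, and it also stands. SAP 3.2 presents the rows as examples: "However, examples were given in the table below showing the probability of 2-sided 95% lower being greater than the CBER thresholds". In Groups 1 and 2 every proportion is the CBER threshold plus 10 or 12 points, so the 10-point age difference simply follows the thresholds (70% v 60%, 40% v 30%). The stratum rows average 0.77, 0.825, 0.47 and 0.60, while the all-ages rows are 0.80, 0.85, 0.50 and 0.55. Group 3 is given higher proportions than the adjuvanted groups, although Protocol 4.3 expects the adjuvant to raise responses. These are separate scenarios and do not estimate an age effect.

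A reader might also infer a gain of around 3% for every contrast from the 0.70 v 0.50 pair (d = 0.5244, 3.4% wider if applied to both groups). The documents do not support that. The pair belongs to Group 3 alone, so it cannot enter Group2/Group1, and the same table halves the gap in Groups 1 and 2. An unequal-variance interval for the Group 3 contrasts would give 0.7% (HAI rows) or 2.7% (seroconversion rows), but that is not the pooled model proposed here, and the 2.7% is driven by that one pair.

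**Conclusion.** The point holds as a small, optional precision gain. The all-ages ratios omit a factor that the design stratifies on, and their intervals are somewhat wider than necessary if titers differ by age. How much is unknown: the documents give a direction for the age effect but no size. The illustrative figure is about 0.8% to 1.4% for all three contrasts. For Group2/Group1 this is worth roughly 1.6% to 2.7% of the sample (d²/4 divided by 1 + d²/4: 0.0159/1.0159 and 0.0276/1.0276). It rests on the example proportions, normal log titers, a common within-stratum SD and equal strata. It would be nil with no age gap and larger with a wide one.

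A reader might infer that the planned intervals are invalid or the ratios biased. Neither follows. Coverage is at or slightly above 95%, and with an even age split in each group the point estimate hardly moves. It is also an inference, though a well-supported one, that all-ages ratios will be reported.

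**What to change.** Before the D43 unblinding, add one sentence to SAP 3.4.2: the all-ages GMT ratios (HIH and SN, D22 and D43) are estimated from a linear model on log10 titer with study group and age stratum, back-transformed, with the unadjusted ratios shown alongside. Leave the per-stratum ratios and the differences in proportions as planned. The same sentence would also make explicit that all-ages ratios are intended.

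The cost is that sentence, one extra table column and one degree of freedom. No new data are needed and no participant is lost, because the age stratum is known for everyone randomised. Protocol 9.4 allows the SAP to be amended before database lock; for the choice to count as pre-specified, it has to be written before the D43 data are unblinded.

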### 9.2 Sample Size Determination Based on HAI Data

Assuming a dropout rate of approximately 10%, a total of approximately 630 participants evaluable for immunogenicity is anticipated.

Table 9.2 shows the expected number of evaluable participants in each study group and each age stratum, and the probability that the lower bound of the 95% CI exceeding the threshold defined by Center for Biologics Evaluation and Research (CBER) requirement for seroconversion and percentage of subjects achieving an HAI antibody titer  $\geq 1:40$  (18).

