**Table 9.2 - Probability calculation**

Age in Years	Evaluable Number of Participants (Study Group)	Expected Proportion	CBER: Lower Bound of 2-Sided 95% CI Greater Than	Probability (%)
Percent of participants with HAI antibody titer <math>\geq 1:40</math>				
$\geq 18$	270 (Groups 1 or 2)	0.80	70%	96%
18 to $< 65$	135 (Groups 1 or 2)	0.82	70%	88%
$\geq 65$	135 (Groups 1 or 2)	0.72	60%	82%
$\geq 18$	90 (Group 3)	0.85	70%	93%
18 to $< 65$	45 (Group 3)	0.85	70%	< 80%
$\geq 65$	45 (Group 3)	0.80	60%	83%
Percent of participants with seroconversion for antibody				
$\geq 18$	270 (Groups 1 or 2)	0.50	40%	90%
18 to $< 65$	135 (Groups 1 or 2)	0.52	40%	< 80%
$\geq 65$	135 (Groups 1 or 2)	0.42	30%	82%
$\geq 18$	90 (Group 3)	0.55	40%	80%
18 to $< 65$	45 (Group 3)	0.70	40%	97%
$\geq 65$	45 (Group 3)	0.50	30%	< 80%

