**Table 1.1: Overall design**

Type of design	Randomized study, enrolling naive participants, 2-dose, modified double-blind. As the study will include adjuvanted study vaccines that may have a different appearance than the unadjuvanted vaccine, personnel assessing the immunogenicity and safety of the investigational vaccines with the goal of dose selection for the pivotal Phase III study in adults
Phase	I/II
Control method	Active comparator (comparator = Panblok H7 (45 µg) unadjuvanted)
Study population	Healthy adults 18 - 64 and $\geq$ 65 years of age
Level and method of blinding	Modified double-blind (participant, Sponsor, and Investigator blinded)
Study intervention assignment method	Randomization and stratification by age group Randomization ratio is: 3:3:1 (Study Group 1, Group 2, and Group 3)
Number of participants	Approximately 700 adult participants (350 adults 18 - 64 years of age and 350 adults $\geq$ 65 years of age)
Intervention groups	Two of the three Investigational Medicinal Products (IMPs) include the MF59 adjuvant.  The IMPs included in this study are: Panblok H7 (7.5 µg) + MF59 (Group 1): Monovalent Recombinant H7 influenza vaccine [A/Guangdong/17SF003/2016 (H7N9)] with MF59  Panblok H7 (15 µg) + MF59 (Group 2):

	
Monovalent Recombinant H7 influenza vaccine [A/Guangdong/17SF003/2016 (H7N9)] with MF59
 
Panblok H7 (45 µg) unadjuvanted (Group 3): Monovalent Recombinant H7 influenza vaccine [A/Guangdong/17SF003/2016 (H7N9)]

Total duration of study participation	A pre-vaccination (baseline) blood sample will be taken during Visit (V) 01 (D01) and post-vaccination blood samples will be taken during V02, V03, V04, and V05 (i.e., D22, D43, D202, and D387) for HIH and SN testing to assess the immune response after Dose 1 and Dose 2 of the study intervention and to assess the persistence of the immune response at 6 and 12 months after the last vaccination
Countries	United States of America
Use of an Independent Data Monitoring Committee, Dose-Escalation Committee, or similar review group	Periodic safety management team (SMT) meetings

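### The between-group HAI and NT titre ratios at D22 and D43 make no use of the scheduled D01 titre; a baseline-adjusted ratio beside them would be a cheap, modest improvement

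*SAP*

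**What the plan says.** For HAI, SAP section 3.4.2 lists "Ratio of GMTs and its 95% CI for: Group1/Group3, Group2/Group3, and Group2/Group1 at D22, and at D43". For the neutralization assay it lists "Ratio of GMs and its 95% CI for: Group1/Group3, Group2/Group3, and Group2/Group1 on D22, and on D43". Protocol section 9.4.2 has the same two items. The interval method is given once for both assays: "using normal approximation of log-transformed for GMs and GMs ratio". No model and no covariate is named. The neutralization item does not say whether the geometric means are of titres or of individual post/D01 ratios.

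D01 is used elsewhere in the plan:
- D01 GMTs and reverse cumulative distribution curves.
- Geometric means of individual post/D01 ratios, listed without a between-group contrast.
- Between-group differences in HAI seroconversion and in NT fold increase, both defined relative to baseline.
- A FAS subgroup description in which "immunogenicity will be described according to sex, race, age subgroups and sero-status at baseline", subject to subgroup size.

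On purpose, SAP section 3.1 states: "All analyses will be descriptive; no hypotheses are planned to be tested".

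**The concern.** Where the baseline value of an outcome is measured and predicts the later value, a comparison of post-dose means that ignores it carries avoidable noise. Here a pre-vaccination sample is scheduled for everyone. Nobody is screened for H7 antibody; exclusion E09 removes only people previously given an investigational H7N9 vaccine. Some participants may therefore start with measurable titres.

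Group 3 is the small arm, with 45 evaluable participants per age stratum, and it is the denominator of two of the three ratios. A few more seropositive participants in one arm would move the ratio. Protocol section 9.5 says the D43 results will help select the formulation. With no test and no decision rule, the point estimates and intervals will be read directly. None of the listed uses of D01 gives a baseline-adjusted titre contrast between groups with an interval.

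**Working it through.** **The plan's own figures.** Allocation: "Randomization ratio is: 3:3:1 (Study Group 1, Group 2, and Group 3". Protocol section 9.2: "Assuming a dropout rate of approximately 10%, a total of approximately 630 participants evaluable for immunogenicity is anticipated". This reproduces: 700 × 0.9 = 630, 150 × 0.9 = 135 and 50 × 0.9 = 45. Table 9.2 sizes the trial only on single proportions against thresholds in the column "CBER: Lower Bound of 2-Sided 95% CI Greater Than". Exact binomial probabilities with Clopper-Pearson limits give, row by row, 95.7, 87.7, 81.7, 92.6, 63.9 and 82.6% for HAI titre ≥ 40, and 89.9, 79.1, 81.7, 80.2, 97.2 and 72.4% for seroconversion. All agree with the stated values. No SD or target precision is given for the GMT ratios, so there is no planned figure to reproduce for them.

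**Assumptions (not in the documents).**
- Residual SD of log10 post-dose titre given D01: 0.6.
- Slope b of post-dose on D01 log10 titre: 0.3 to 0.9.
- Share q seropositive at D01: 0, 3% or 10%.
- Seropositive D01 titres: 20, 40 or 80 in equal parts.
- Everyone else at 5. The SAP sets values below the LLOQ to half of it. The protocol states an LLOQ of 10 for the neutralization assay, and I assume the same for HAI.

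**Baseline variance.** Relative to a titre of 5, the seropositive values are log10 4 = 0.602, log10 8 = 0.903 and log10 16 = 1.204. Their mean is 0.903 and their mean square is 0.876. So Var(D01) = 0.876q − (0.903q)².
- q = 3%: 0.0263 − 0.0007 = 0.0256 (SD 0.160)
- q = 10%: 0.0876 − 0.0082 = 0.0794 (SD 0.282)

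**Precision.** The unadjusted SD is √(0.36 + b² × Var(D01)); after adjustment it is 0.6. For Group 1 or 2 against Group 3 in one age stratum, √(1/135 + 1/45) = 0.1721. The adjusted 95% CI factor is 10^(1.96 × 0.6 × 0.1721) = 1.59.

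| q | b | Unadjusted SD | CI factor, unadjusted | CI factor, adjusted | Fall in log half-width |
|---|---|---|---|---|---|
| 0 | any | 0.600 | 1.59 | 1.59 | 0% |
| 3% | 0.3 | 0.602 | 1.60 | 1.59 | 0.3% |
| 3% | 0.9 | 0.617 | 1.62 | 1.59 | 2.8% |
| 10% | 0.3 | 0.606 | 1.60 | 1.59 | 1.0% |
| 10% | 0.9 | 0.651 | 1.66 | 1.59 | 7.9% |

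Rounded, that is 0-3% at 3% seropositive and 1-8% at 10%. A simulation of the three-group model (135, 135 and 45), which includes the cost of estimating the slope, gave empirical SE ratios of 0.997 and 0.975 at 3%, and 0.995 and 0.922 at 10%. These are close to the formula.

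**Chance imbalance.** The 95% limit of the D01 difference between arms is 1.96 × SD(D01) × 0.1721 on the log10 scale: 0.054 at q = 3% and 0.095 at q = 10%. Multiplied by b, this moves the GMT ratio by a factor of 1.04 to 1.12 at 3%, and 1.07 to 1.22 at 10%. A more concrete case is two extra seropositives among the 45, at titre 40 rather than 5. They move the ratio by 10^(2/45 × 0.903 × b), a factor of 1.03 to 1.09, against an unadjusted CI factor of about 1.6.

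**The case against.** The case against any change is substantial, and most of it stands.

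- **Chance imbalance is not bias.** Randomization is stratified by age, and the unadjusted interval already allows for chance variation in D01. A reader might infer that the planned ratios are biased or their intervals wrong; the documents do not support that. Adjustment only corrects the estimate for the imbalance actually seen.
- **The population is mostly naive.** SAP Table 1.1 describes the enrolled participants as naive, and protocol section 4.2 expects most to be. With values below the LLOQ set to one constant, D01 may hardly vary. The planned serostatus subgroup is conditional on numbers, so it is not evidence that the sponsor expects variation.
- **Little hangs formally on the GMT ratio.** Sizing and the threshold-based interpretation concern HAI ≥ 40 and seroconversion. The analyses are descriptive, and two between-group contrasts already use baseline. Those contrasts are dichotomized, however, so they do not replace an adjusted titre ratio.
- **D01 can be missing.** SAP section 4.2.1 foresees this, and the FAS does not require a D01 sample.

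A stronger reading is also tempting. Table 9.2 pairs 80% with HAI ≥ 40 and 50% seroconversion. Anyone at ≥ 40 who has not seroconverted must have had D01 above 10, so a reader might infer at least 30% seropositive and a correspondingly large gain. The SAP presents these rows as examples of what follows if a proportion is reached. They do not cohere as a joint forecast: equal age strata at 0.82 and 0.72 average 0.77, not 0.80, and 0.52 and 0.42 average 0.47, not 0.50. The 30-point gap equals the gap between the thresholds (70 less 40, 60 less 30), and for Group 3 aged 18 to < 65 it is 15 points (0.85 less 0.70). The table cannot support 30% seropositivity.

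**Conclusion.** The point holds as a minor, optional improvement. The plan specifies no baseline-adjusted between-group titre ratio for either assay, although the data for one are already scheduled. The size is conditional: no gain if all are naive, and otherwise the ranges in the table above, with the documents pointing towards the low end. The SD, slope, seropositive share and D01 titre values behind those ranges are all assumed.

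The better reason to prespecify is imbalance. If D01 titres happen to differ between a large arm and the 45 in Group 3, an adjusted ratio named before the D43 unblinding avoids a post hoc choice. The neutralization wording needs settling in any case.

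**What to change.** In SAP 3.4.2:
- Obtain the HAI and NT GMT ratios at D22 and D43 from a linear model of log10 titre on group and log10 D01 titre (same assay), fitted within each age stratum. Back-transform the adjusted group difference and its 95% CI.
- Keep the unadjusted ratios and intervals alongside.
- State that the neutralization ratio of geometric means refers to titres.
- State that participants without a D01 result drop from the adjusted ratio only, and that if D01 is constant in a stratum the adjusted ratio reduces to the unadjusted one.

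The cost is a few sentences in the SAP and one standard model per assay, visit and stratum, with no new samples or visits. The small downside is the loss of participants without a D01 result from the adjusted ratio.
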